**Permitted windows for assessments before Day 1 of Cycle 1:**

If physical examination, ECOG PS, vital signs, Hematology, Biochemistry-A, Biochemistry-B, CLcr (provided only if serum creatinine levels are above ULN) and Coagulation were assessed  $>10$  days before Day 1 of Cycle 1, the tests must be repeated the day before or the Day 1 (always prior to lorbinecetin infusion).

If pregnancy test was done  $>7$  days before Day 1 of Cycle 1, the test must be repeated the day before or the Day 1 (always prior to lorbinecetin infusion).

A patient should only be treated if eligibility criteria are still met according to assessments performed closest to treatment start.

**Permitted windows for assessments after Day 1 of Cycle 1:**

A  $\pm 2$ -day time window will be allowed for Hematology, Biochemistry-A and CLcr (provided only if serum creatinine levels are above ULN) on Day 8 and Day 15, and for vital signs on Day 8 of Cycle 1.

A -1 day window will be allowed for physical examination, ECOG PS, vital signs, Hematology, Biochemistry-A, and Biochemistry-B, CLcr (provided only if serum creatinine levels are above ULN) and Pregnancy test on Day 1 of Cycle 2 and further cycles (always prior to lorbinecetin infusion).

A + 2 days window for Day 1 lorbinecetin administration of Cycle 3.

If a drug administration is delayed beyond the permitted protocol window, assessments planned for the original administration day must be repeated on the day the dose is finally administered.

a BSA calculated according to DuBois formula (see [Appendix 4](#)).

b Any patient having any grade  $\geq 3$  laboratory abnormalities and/or treatment-related AEs is suggested to have the relevant tests re-assessed at intervals of at least 72 hours but not more than one week (for patients allocated to Sequence 1) or at least every 48-72 hours (for patients allocated to Sequence 2) until recovery to at least grade 2 has been documented.

c Calculated CLcr [Cockcroft and Gault's formula] should be provided only if serum creatinine levels are above ULN.

d "On treatment period" = from first administration of the study treatment (itraconazole or lorbinecetin) to the last lorbinecetin administration (and maximum of three cycles) plus 31 days (EOT). Follow-up period will be extended every four weeks until recovery to at least grade 1 or stabilization of all treatment-emergent AEs, or until the start of a new antitumor therapy, until the continuation of treatment outside this study under a Compassionate Use Agreement or death, whichever occurs first.

e The "AE form" will be used only for events that occur after the first drug infusion or any event related to a study procedure within the study period (according to ICH guidelines); and to report 'ongoing' baseline conditions in case of any significant change (improvement or worsening) during the study.

ASSESSMENT	TIME
AAG, alpha 1-acid glycoprotein; AEs, adverse events; ALT, alanine aminotransferase; AP, alkaline phosphatase; AST, aspartate aminotransferase; BSA, body surface area; CLcr, Creatinine clearance; CPK, creatine phosphokinase; CPK-MB, creatine phosphokinase-isoenzyme MB; CRP, c-reactive protein; ECG, electrocardiogram; ECHO, echocardiogram; EOI, end of infusion; EOT, end of treatment; GGT, gamma glutamyltransferase; ICH, International Conference on Harmonization; IL-6, interleukin 6; INR, International Normalized Ratio; LDH, lactate dehydrogenase; LVEF, left ventricular ejection fraction; MUGA, multiple-gated acquisition scan; NCI-CTCAE, National Cancer Institute-Common Terminology Criteria for Adverse Events; PK, pharmacokinetics; RT, reference-test; SOI, start of infusion; TR, test-reference sequence; ULN, upper limit of normal; WBC, white blood cells; WOCBP, woman of childbearing potential.	

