## **7.4 Treatment Administration**

Exposure to treatment will be described by sequence treatment group.

Total cumulative dose, time on treatment, dose intensity and relative dose intensity, administration delay and dose reductions/omissions will be described following standard

tables (detailed in Section 11, Appendix II). The reported cycle information on the case report form (CRF) pages will be used for the analysis.

Time on treatment, expressed in weeks, is defined as the last administration date of lurbinectedin minus the first administration date of lurbinectedin plus 31 days, except if the patient dies or starts a new antitumor therapy within 31 days from the last administration date, in which case the time on treatment will be the date of death or the start date of the new antitumor therapy minus the date of the first administration of the study treatment.

Total cumulative dose by drug, expressed in mg for both lurbinectedin and itraconazole, is the sum of all the product doses received during the study, including the dose received in the last cycle.

For lurbinectedin, intended dose intensity is the planned dose per cycle divided by the planned number of weeks by cycle.

Absolute dose intensity is the actual cumulative dose divided by the number of weeks of treatment. As a convention, for this calculation, the duration of the last cycle will be the predefined cycle length (e.g, 21 days). Relative dose intensity (%) is the ratio of absolute dose intensity divided by the intended dose intensity. In those cases where the relative dose intensity is over 100% due to permitted dose anticipation (i.e. patients receiving more dose than planned), this ratio will be adjusted to 100%.

The options “Dose Reduced” and “Dose Delayed” available in the Treatment Modification item on the treatment exposure CRF pages will be used to calculate delays and dose reductions, respectively. For cycles considered as delayed by the Investigator, the length of the delay will be calculated as:

Duration of cycle delay: Date of the current drug administration – Date of the previous drug administration – the predefined cycle length (i.e., 21 days).

For itraconazole, the percentage of compliance will be calculated by dividing the actual total dose by the intended dose.

If the number of delays or dose reductions are very low, tables will not be presented and only listings will be shown.

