#### 11.1.1 Treatment Administration

Table 11.1.1.1 Number of cycles administered†

No. of cycles administered	Part A		Part B		Part A+B		Total	
	S1 (TR)		S1 (TR)		S2 (RT)			
	N	%	N	%	N	%		
1 cycle								
2 cycles								
3 cycles								

Notes: Percentage is based on number of patients by study part and sequence, when applicable.

† Including when lorbinecetin is administered both alone and in combination with itraconazole.

Part A, patients assigned to Sequence 1; Part B, sequence assigned randomly.

S1, Sequence 1; S2, Sequence 2; TR, test-reference; RT, reference-test.

Table 11.1.1.2 Summary of number of cycles administered† and time on treatment

No. of cycles administered per patient	Part A		Part B		Part A+B		Total	
	S1 (TR)		S1 (TR)		S2 (RT)			
	N	Median (range)	N	Median (range)	N	Median (range)		
Time on treatment (weeks)*								
N								
Median (range)								

Notes: Percentage is based on number of patients by study part and sequence, when applicable.

† Including when lorbinecetin is administered both alone and in combination with itraconazole.

\*Time on treatment is defined as the last administration date of lorbinecetin plus 31 days, death or the start date of the new therapy, whichever comes first, minus the first administration date of lorbinecetin.

Part A, patients assigned to Sequence 1; Part B, sequence assigned randomly.

S1, Sequence 1; S2, Sequence 2; TR, test-reference; RT, reference-test.

Table 11.1.1.3 Dose information by study part and sequence

Cumulative dose (mg/m  )	Part A		Part B		Part A+B		Total	
	S1 (TR)		S1 (TR)		S2 (RT)			
	N	Median (range)	N	Median (range)	N	Median (range)		
Dose intensity (mg/m  /week)								
N								
Median (range)								
Relative dose intensity (%)								
N								
Median (range)								

	Part A	Part B	Part A+B	Total
	S1 (TR)	S1 (TR)	S2 (RT)	
Cumulative dose (mg)			Itraconazole	
N				
Median (range)				
Compliance (%)				
N				
Median (range)				

Notes: Percentage is based on number of patients by study part and sequence, when applicable.

Part A, patients assigned to Sequence 1; Part B, sequence assigned randomly.

S1, Sequence 1; S2, Sequence 2; TR, test-reference; RT, reference-test.

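### SAP 7.4 counts time on treatment from first lurbinectedin, but from first study treatment after death or new therapy, which adds 4 to 6 days in Sequence 1

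*Protocol*

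**What the plan says.** SAP 7.4 (Treatment Administration) gives a main rule and an exception.

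- Main rule: time on treatment is "defined as the last administration date of lurbinectedin minus the first administration date of lurbinectedin plus 31 days".
- Exception: the main rule applies "except if the patient dies or starts a new antitumor therapy within 31 days from the last administration date". In that case the duration is the date of death or the "start date of the new antitumor therapy minus the date of the first administration of the study treatment".

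The footnote to SAP Table 11.1.1.2, the table that reports the variable, states it differently. The end is the earliest of last lurbinectedin plus 31 days, death or new therapy, "whichever comes first, minus the first administration date of" lurbinectedin. It has one origin for every patient.

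SAP 7.4 does not say what study treatment means. The protocol does: section 5.2 and footnote d of Table 5 (section 6.4) start the on-treatment period "from first administration of the study treatment (itraconazole or" lurbinectedin). Protocol 3.1 starts itraconazole four days before the infusion, and Sequence 1 gives it in Cycle 1.

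**The concern.** A duration needs one origin. Here the origin depends on how the patient's treatment ended. In Sequence 1 the two possible origins are at least four days apart, so the patients whose follow-up is cut short are also the ones whose clock starts earlier. Part of the intended shortening is cancelled. When the event comes late in the 31-day window, the sign reverses, and a patient who died is shown with more time on treatment than one who did not.

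The SAP also contradicts itself. A programmer working from section 7.4 and one working from the Table 11.1.1.2 footnote will produce different values for the same patient. The outputs at stake are Table 11.1.1.2, which shows a median and range by study part and sequence, and the time-on-treatment column of Listing 11.3.2.2 (Deaths). Three patients are planned in Part A and eight, randomized 1:1, in Part B. Cells are therefore of three or four, and one value can move a median or a range.

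**Working it through.** **Inputs**

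- L, the lead from first itraconazole to first lurbinectedin in Sequence 1. Protocol 3.1 gives 12 consecutive days of itraconazole from Day -4 to Day 8. Check: Days -4 to -1 are 4 days and Days 1 to 8 are 8 days; 4 + 8 = 12, as stated, so there is no Day 0 and L = 4.
- The same section allows up to 14 days of itraconazole if lurbinectedin is delayed by up to 2 days, and the Sequence 1 schedule applies this to Cycle 1. So L can reach 4 + 2 = 6.
- S, last minus first lurbinectedin date. With the 21-day cycle of SAP 7.4, S = 0 for one cycle and 21 for two on-time cycles.
- d, days from last lurbinectedin dose to death or new therapy. I take day 31 as within 31 days.

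**Formulas**

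- Main rule: S + 31.
- Exception as written: S + d + L.
- Table 11.1.1.2 footnote: S + the smaller of d and 31.
- Exception minus footnote: (S + d + L) - (S + d) = L. This holds for every Sequence 1 exception case, whatever S and d.
- The exception exceeds the main rule when S + d + L > S + 31, that is d > 31 - L. With L = 4 this is d = 28 to 31; with L = 6, d = 26 to 31. The excess is d + L - 31, so 1 to 4 days or 1 to 6 days, for any number of cycles.

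**Results in days, Sequence 1**

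| Case | One cycle, L = 4 | Two cycles, L = 4 | Two cycles, L = 6 | Two cycles, footnote |
|---|---|---|---|---|
| No death or new therapy | 31 | 52 | 52 | 52 |
| Event at d = 10 | 14 | 35 | 37 | 31 |
| d = 25 | 29 | 50 | 52 | 46 |
| d = 26 | 30 | 51 | 53 | 47 |
| d = 27 | 31 | 52 | 54 | 48 |
| d = 28 | 32 | 53 | 55 | 49 |
| d = 30 | 34 | 55 | 57 | 51 |
| d = 31 | 35 | 56 | 58 | 52 |

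The SAP reports the variable in weeks. For two cycles with L = 4 and d = 30, the exception gives 55/7 = 7.86 weeks, against 52/7 = 7.43 for a patient without the event. The footnote gives 51/7 = 7.29.

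**Sequence 2.** The first study treatment is lurbinectedin, so L = 0. The exception gives S + d, which cannot exceed S + 31.

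**With lurbinectedin as the origin in both branches.** The exception becomes S + d, at most S + 31. No inversion is possible, and section 7.4 then agrees with the footnote in every case.

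**The case against.** The best defence is that this is a slip in one clause. The main rule and the table footnote both say lurbinectedin, SAP 7.4 leaves study treatment undefined, and a programmer working from the footnote would never produce the wrong value. The inversion needs a late event and may affect no patient. The variable is descriptive: the PK comparison and the safety comparisons do not use it, dose intensity sets the last cycle at its predefined length, and the deaths listing also shows time from first and last dose. All of this stands, and it limits the size of the point. It does not make the clause right. The sentence changes its term partway through, and the protocol's definition gives that term a different date in Sequence 1.

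A reader might infer something stronger: that time on treatment should start at first itraconazole, as the protocol's on-treatment period does, so that two on-time Sequence 1 cycles are reported 4 days short (52 against 56, or 4/56 = 7.1%), that all 3 + 4 = 7 of 11 planned Sequence 1 patients are affected, and that the sequences are not compared like for like. The documents do not support this.

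- The protocol period in Table 5 is the window for recording adverse events, intercurrent events and concomitant therapies. It is not an exposure measure.
- The SAP reports itraconazole exposure separately, as cumulative dose and compliance. Its exposure tables use the safety population, which requires a lurbinectedin dose. Starting at lurbinectedin is a coherent choice.
- Under the main rule, two on-time infusions score 52 days in either sequence, because the Sequence 2 itraconazole lead-in falls between its two infusions. An itraconazole origin would give 56 days in Sequence 1 and 52 in Sequence 2, a difference due to treatment order alone.

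Nor does early death in general lengthen time on treatment relative to a survivor: a one-cycle death at day 10 scores 14 days against 31.

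**Conclusion.** The point holds, as a minor one. For every Sequence 1 patient who dies or starts new therapy within 31 days of the last dose, SAP 7.4 as written overstates time on treatment by 4 days, or by up to 6 with the permitted delay. It contradicts the Table 11.1.1.2 footnote by the same amount. Such a patient outscores one without the event only in the last four days of the window (the last six with the delay).

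This rests on three assumptions: that study treatment in SAP 7.4 carries the protocol's meaning of either drug; that section 7.4 rather than the footnote is programmed; and that day 31 falls inside the window. If the footnote is programmed, the values are right and only the contradiction in the text remains. If day 31 is outside, the inversion stops at day 30 and the largest excess is 3 days (5 with the delay).

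**What to change.** In the exception clause of SAP 7.4, replace the reference to the first administration of study treatment with the first administration of lurbinectedin. Both branches and the Table 11.1.1.2 footnote then share one origin. Label the variable as lurbinectedin time on treatment in SAP 7.4, Table 11.1.1.2 and Listing 11.3.2.2, so that it is not mistaken for the protocol's on-treatment period. No protocol change is needed. The cost is a few words in one SAP sentence and the output labels, with no new data.

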## 6.5 EVALUATIONS AT THE END OF TREATMENT

The end-of-treatment (EOT) visit will be scheduled within 31 days ( $\pm 10$  days) after administration of the last dose of lurtinectedin, unless the patient starts a subsequent antitumor therapy, in which case the end-of-treatment visit should be performed immediately before the start of the new therapy (ideally the day before or the same day).

Patients who meet the continuation criteria and obtain a clear clinical benefit with lurtinectedin after the completion of the first two study cycles, may continue treatment outside this study under a Compassionate Use Agreement after the completion of the optional third study cycle. Should the patient continue under a Compassionate Use Agreement, the treating center must request authorization to the relevant Health Authorities and notify the Sponsor in due time. Patients, regardless of the reason for ending the treatment, will have to undergo at the end of treatment the following assessments:

- Complete physical examination (BSA and height not needed).
- ECOG PS.
- Laboratory tests (hematology and biochemistry A and B, and Calculated CLcr). Calculated CLcr [Cockcroft and Gault's formula] should be provided only if serum creatinine levels are above ULN.
- Coagulation (INR) will be repeated only if clinically indicated.
- ECG (in triplicate).
- LVEF assessment will be repeated only if clinically indicated.
- Adverse Events.
- Intercurrent events, concomitant disease and therapies.
- Pregnancy test in WOCBP.

Adverse events must be reported for 31 days after the last study treatment administration. All serious adverse events (SAEs) occurring within 31 days of the last study treatment administration or until the start of a new antitumor therapy, until the continuation of treatment outside this study under a Compassionate Use Agreement or death, whichever occurs first, will be reported. Beyond this period of time, only those suspected to be treatment-related SAEs will be reported (Section [8.5.2](#)).

The Sponsor will evaluate all safety information that is spontaneously reported by an Investigator beyond the time frame specified in the protocol.

## 6.6 FOLLOW-UP AFTER END OF-TREATMENT VISIT

After EOT, patients with treatment-related toxicities  $>$  grade 2 will be followed every four weeks until recovery to at least grade 1 or stabilization of all treatment-emergent

AEs, or until the start of a new antitumor therapy, until the continuation of treatment outside this study under a Compassionate Use Agreement or death, whichever occurs first.

## 7. TREATMENT

### 7.1 DESCRIPTION OF TREATMENT

All patients will receive two consecutive cycles of lurbinecetin, one cycle with and one cycle without itraconazole co-administration (in different order depending on the study sequence of treatment), followed by a third cycle with lurbinecetin alone (this last cycle optional for patients with clinical benefit). This study will consist of two parts, Part A and B as described in Section [3.1](#).

#### 7.1.1 Drug Formulation and Supply

##### Itraconazole

Commercially available itraconazole capsules (with strengths of 100 mg) will be provided by the Sponsor.

##### Lurbinecetin

Lurbinecetin drug product (DP) is presented as a lyophilized powder for concentrate for solution for infusion in 4 mg vials and will be supplied by the Sponsor for the purposes of this study.

[REDACTED] For administration to patients as an i.v. infusion, reconstituted vials should be diluted with either glucose 50 mg/mL (5%) or sodium chloride 9 mg/mL (0.9%) solution for infusion.

The full composition of the lurbinecetin 4 mg vials and the reconstituted solution per mL is shown below:

[REDACTED]	[REDACTED]	[REDACTED]

For detailed instructions on the reconstitution and dilution, refer to the latest lurbinecetin IB and the “Preparation Guide for Infusion” document.

#### 7.1.2 Storage Conditions

##### Itraconazole

Itraconazole capsules should be stored following the instructions described in the SmPC.

## **Lurbinectedin**

Until more information is available from ongoing stability studies, lurbinectedin DP 4 mg should be stored at  $+5^{\circ}\pm 3^{\circ}\text{C}$ .

## **7.2 ADMINISTRATION OF THE STUDY MEDICATION**

### **Itraconazole**

Itraconazole will be administered orally once daily as 200 mg (2 capsules of 100 mg).

In the co-administration cycles, itraconazole will be administered orally once daily in the morning after breakfast during 12 consecutive days, self-administered at home from Day -4 (i.e., four days before lurbinectedin infusion) until Day 8 (i.e., seven days after lurbinectedin infusion), and supplied at the study center on Day 1, following recommendations at the Summary of Product Characteristics (SmPC). On Day 1 (i.e., day of lurbinectedin infusion), itraconazole will be given immediately prior to the start of the lurbinectedin infusion. In fact, itraconazole should be administered after obtaining the itraconazole PK sample #1 and before the start of lurbinectedin infusion (-15 min to -1 min). In case of lurbinectedin delay ( $\leq 2$  days), itraconazole could be administered during a maximum of 14 days.

In Sequence 1 (TR), itraconazole for self-administration and the patient's diary should be given to the patient on Day -5 with a -2/+1 day time window (i.e., from Day -7 to Day -4). In Sequence 2 (RT), itraconazole and the patient's diary should be given to the patient on Day -5 of Cycle 2 with a -2/+1 day time window (i.e., from Day 15 of Cycle 1 to Day -4 of Cycle 2).

In addition, the study center will contact the patients (via telephone or other methods) daily during itraconazole intake to remind them or confirm that they have taken the morning dose of itraconazole when they are not at the study center.

### **Lurbinectedin**

Lurbinectedin will be administered as a 1-hour (-5/+20 min) i.v. infusion on Day 1 q3wk, [REDACTED]

Patients will receive a maximum of three cycles: two consecutive cycles of lurbinectedin, one cycle with and one cycle without itraconazole co-administration (in different order depending on the Sequence 1 or Sequence 2 of treatment), followed by a third cycle with lurbinectedin alone (this last cycle optional for patients with clinical benefit).

The dose of lurbinectedin when given in combination with itraconazole for the initial three patients in Part A will be 0.8 mg/m^2. Lurbinectedin dose in Part B will be based on the acceptability of the PK and safety results from the first three patients in Part A.

In cycles with lurbinectedin as single agent, lurbinectedin will be administered at 3.2 mg/m^2.

## **7.3 PROPHYLACTIC MEDICATION**

All patients will receive standard antiemetic prophylaxis before each treatment infusion (i.e., 30  $\pm$  5 minutes before lurbinectedin administration), i.v. as follows:

- Corticosteroids i.v. (according to institutional standard antiemetic doses, minimum dose of dexamethasone 8 mg/day and maximum dose of 20 mg/day of dexamethasone or equivalent). If feasible, the medication and dose administered in Cycle 1 should be maintained in Cycle 2.
- Serotonin (5-HT3) antagonists (ondansetron at least 8 mg i.v. and no more than 16 mg of ondansetron).

If necessary, in addition to the above, the duration of treatment with 5-HT3 antagonists and/or dexamethasone could be extended orally (if needed) (i.e., 4-8 mg/day for three consecutive days) and/or 10 mg of metoclopramide orally every eight hours could be added (according to institutional guidelines).

For the purpose of safety evaluations, optimum prophylaxis is defined as all the aforementioned medications at their respective maximum dose.

**Aprepitant or any other NK-1 antagonist or related Substance P-antagonists (except rolapitant) are forbidden while on lorbinecetin treatment.**

